**“EVALUATION OF THE EFFECT OF COCOA SUPPLEMENTATION ON THE
BIOCHEMICAL AND CLINICAL PROFILE AND SENSORY-MOTOR PROCESSING OF
PERIPHERAL AND AUTONOMIC DIABETIC NEUROPATHY: RANDOMIZED CLINICAL
TRIAL”**

NCT05247034

March 25 2025, last update

SUMMARY

Background: Type 2 diabetes (T2D) is a highly prevalent disease in Mexico and is associated with the development of chronic-degenerative complications such as diabetic neuropathy. The latter manifests as a set of disorders that occur as a consequence of a chronic hyperglycemic state that can induce oxidative stress and inflammation, resulting in damage to the autonomic and peripheral nervous systems. Diabetic neuropathy increases the risk of pain and skin lesions, ulcers, or even amputations, affecting the quality of life of those who suffer from it. In Mexico, it has been reported that this complication occurs in 29% to 90% of patients with diabetes. Cocoa is a food with a high flavonoids content, which are phenolic compounds with antioxidant and anti-inflammatory effects. Additionally, its consumption has been associated with decreased hyperglycemia and insulin resistance, improved mitochondrial function, and, based on the above, a potential effect on diabetic complications has been suggested. This has been demonstrated in *in vivo* and *in vitro* models but not in human populations. Once symptoms of diabetic neuropathy appear, palliative treatments are prescribed, as no pharmacological compounds have yet been shown to reverse the consequences of peripheral and autonomic diabetic neuropathy. Additionally, clinical trials of compounds with antioxidant properties have only conducted subjective evaluations based on questionnaires about perceived improvement in diabetic neuropathy and some biochemical markers or nerve conduction tests, with inconclusive results. **Methodology:** A double-blind, randomized, controlled clinical trial is proposed to evaluate the effect of cocoa supplementation in patients with type 2 diabetes and peripheral and autonomic diabetic neuropathy on a) the biochemical profile, including the assessment of glycemic and lipid profiles, b) the clinical profile through standardized questionnaires, anthropometric measurements, and blood pressure; and c) somatosensory processing through the rate-dependent depression of the H-reflex test. **Hypothesis:** The hypothesis of this study is that cocoa supplementation will have a beneficial effect on the biochemical and clinical profile and somatosensory processing of peripheral and autonomic diabetic neuropathy. **Statistical analysis:** For the evaluation of intra-group variables, a statistical analysis will be performed using repeated measures ANOVA with Tukey *post hoc*, or if applicable, Friedman with Dunn *post hoc*, as well as Student's t-test for dependent groups, or if applicable, Wilcoxon. The intergroup comparison will be made with Student's t-test for

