2.5 Diagnosis

Patients with DM should be evaluated for diabetic neuropathy at diagnosis and for 5 years thereafter, and an annual review is recommended through a detailed clinical history, physical examination, and clinical tests. (14) The diagnosis of DN is made when other causes that could be causing the signs and symptoms are excluded and can be supported by tools such as questionnaires and tests. (16)

Among the causes of neuropathy that must be excluded to make the diagnosis are toxic or drug-induced neuropathy, alcoholic neuropathy, neuropathy associated with HIV, hypothyroidism, and neuropathy due to vitamin B12 deficiency. Especially, those subjects who take metformin as a pharmacological treatment for T2D are at high risk of developing vitamin B12 deficiency since it decreases the absorption of this vitamin in the terminal ileum and is related to alterations in intrinsic factor levels. (28, 29) The signs and symptoms of vitamin B12 deficiency are very similar to those observed in diabetic neuropathy, and therefore, their differentiation can be complex. Thus, the determination of serum vitamin B12 is suggested to exclude non-diabetic causes of neuropathy. (29)

On the other hand, among the tools that can support the diagnosis of DN are biopsy, which is an invasive test; nerve conduction tests, which are expensive and are only useful to evaluate fast conduction fibers, which are not very practical; and the sensory test with the monofilament. (30)

The Michigan Neuropathy Screening Instrument (MNSI) is a validated tool available in Spanish, which evaluates the presence of diabetic peripheral neuropathy. This instrument can be applied quickly, includes the history of symptoms and physical examination to detect alterations in the foot. It has a sensitivity of 65% and specificity of 83%, and a score of ≥ 2 has been proposed as a cut-off point for the diagnosis of DPN. (31, 32)

Another tool that allows the severity of DN to be evaluated is the Toronto Clinical Scoring System (TCSS), which evaluates the symptoms, reflexes, and sensitivity by anatomical

regions. According to the score obtained, 3 grades are established: 0-5 points, no DN; 6-8 points, mild DN, 9-11 points, moderate DN and 12-19 points, severe DN. (33, 34)

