6. HYPOTHESIS

Cocoa supplementation has a beneficial impact on the biochemical and clinical profile and somatosensory processing of diabetic peripheral and autonomic neuropathy.

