7.1 SPECIFIC OBJECTIVES

Biochemical profile:

- To evaluate the effect of cocoa supplementation on the glycemic profile (HbA1c and fasting blood glucose).
- To evaluate the effect of cocoa supplementation on lipid profile (triglycerides, HDL-c, LDL-c and TG/HDL).
- To evaluate the effect of cocoa supplementation on markers of inflammation (neutrophil/lymphocyte ratio).

Clinical profile:

- To evaluate the effect of cocoa supplementation on the “Toronto Clinical Scoring System” score.
- To evaluate the effect of cocoa supplementation on anthropometry (weight, waist and abdominal circumference, waist to height ratio).
- To evaluate the effect of cocoa supplementation on blood pressure.
- To evaluate the effect of cocoa supplementation on quality of life.
- To evaluate the effect of cocoa supplementation on gastrointestinal symptoms.

Somatosensory processing:

- To evaluate the effect of cocoa supplementation on sensorimotor processing in the spinal cord using the RDD of the H reflex test.

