8.5 Selection criteria

Inclusion Criteria	Non-inclusion Criteria

 - Adults aged 40-60 years with a diagnosis of type 2 diabetes mellitus (T2D) and diabetic neuropathy - Minimum duration of T2DM diagnosis: 5 years. - MNSI (Michigan Neuropathy Screening Instrument) score ≥ 2. - Both genders. - Must sign the informed consent form 	
 - Subjects with known sensitivity or hyperreactivity to cocoa or any of its components. - Pregnant women. - Subjects with neurological diseases, such as multiple sclerosis, epilepsy, or previous cerebrovascular events. - Subjects with implanted electronic devices, e.g., pacemakers. - Subjects with peripheral nerve damage in the lower extremities caused by trauma.

	
 - Subjects with a diagnosis of disc herniation below T10. - History/diagnosis of herpes zoster. - Serological diagnosis of rheumatoid arthritis or systemic lupus erythematosus. HIV/AIDS. - Venous insufficiency (C2-C6 class, asymptomatic/symptomatic according to Nicolaides CEAP classification) in lower limbs. - Clinical hypothyroidism. - Use of orthopedic equipment (e.g., prosthetics, splints, wheelchair, crutches). - Cancer diagnosis, use of oncological drugs and/or radiotherapy, or history of cancer or tumors treated with oncological drugs or radiotherapy. - Smoking, considered positive in those with a smoking index greater than 10. - History of diabetic foot (Wagner Scale 3-5) or amputation. - Presence of ulcers and open and/or extensive wounds (>2 cm) - Allodynia - Sciatic nerve root compression - Gout/Hyperuricemia
--	---

Elimination Criteria

- Subjects who modify their pharmacological treatment during the study.
- Subjects who do not attend one of the intermediate consultations
- Subjects who withdraw informed consent or decide not to continue participating in the

study

- Subjects with less than 80% adherence to cocoa supplementation
- Subjects who miss more than one consultation or do not attend the final consultation.

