Appendix 5: BEST questionnaire

TABLA 2. Cuestionario BEST para evaluar el impacto de los síntomas de un intestino irritable sobre la CVRS

1. Durante las últimas 4 semanas, ¿Cómo se ha sentido en relación a su hábito de defecar?
 - Muy bien: mis deposiciones han sido normales.
 - Bien: apenas ha habido alteraciones en mi ritmo intestinal y, de hecho, las he ignorado.
 - Regular: no he podido ignorar las alteraciones en mi ritmo intestinal.
 - Mal: las alteraciones de mi ritmo intestinal han llegado a afectar a mi estilo de vida.
 - Muy mal: las alteraciones del ritmo intestinal han afectado gravemente a mi estilo de vida.
2. Lea Vd. la siguiente declaración y diga lo que opina sobre ella: "Los síntomas intestinales que estoy sufriendo significan que algo muy serio está ocurriendo en mi cuerpo".
 - No, de ninguna manera.
 - Sí, quizás en algún momento, pero muy pocas veces.
 - Sí, algo sí.
 - Sí, bastante.
 - Sí, mucho.
3. Durante las últimas 4 semanas, ¿con qué frecuencia sus síntomas intestinales han hecho que se sienta tenso o profundamente afectado?
 - La mayoría del tiempo.
 - En muchas ocasiones.
 - Solo muy de vez en cuando.
 - En ningún momento.
4. Díganos lo que piensa sobre la siguiente frase: "Debido a los síntomas intestinales que sufro, durante las últimas 4 semanas no he podido disfrutar de las cosas que antes me divertían".
 - De ninguna manera me ha ocurrido esto.
 - Sí, quizás en algún momento, pero muy pocas veces.
 - Sí, algo sí.
 - Sí, bastante.
 - Sí, mucho.

Las respuestas a estas preguntas se miden en una escala de 0 (el mejor estado de salud) a 100 (el peor estado de salud). La calificación final asignada de acuerdo a un algoritmo estándar se entrega al médico, antes de que éste entre en la consulta. [Spiegel BMR, Naliboff, Mayer E, et al. Development and initial validation of a concise point-of-care IBS severity index: the 4-item BEST questionnaire. *Gastroenterology* 2006;130:S1040].

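### The plan claims an effect on autonomic neuropathy, but entry does not require it and the only measures assigned to it are bowel-symptom tools, so only a claim about gastrointestinal symptoms can be supported.

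*Combined protocol and SAP*

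**What the plan says.** **Claim.** The summary sets out "to evaluate the effect of cocoa supplementation in patients with type 2 diabetes and peripheral and autonomic diabetic neuropathy". Section 6 states: "Cocoa supplementation has a beneficial impact on the biochemical and clinical profile and somatosensory processing of diabetic peripheral and autonomic neuropathy". The title, the research question (5) and the general objective (7) also join peripheral and autonomic neuropathy.

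**Entry.** Section 8.5 requires adults "with a diagnosis of type 2 diabetes mellitus (T2D) and diabetic neuropathy" and an "MNSI (Michigan Neuropathy Screening Instrument) score" of at least 2. Section 2.5 describes the MNSI as a tool "which evaluates the presence of diabetic peripheral neuropathy". Section 8.7 names it as the instrument applied at baseline as part of diagnosing neuropathy.

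**Measurement.** The 8.6 variable table defines autonomic neuropathy as nerve damage affecting the cardiovascular, gastrointestinal and urogenital systems, among others. It then assigns two measures: the BEST questionnaire and the Bristol scale. Section 2.5 says there is no standard for assessing autonomic neuropathy and offers these two as tools for its gastrointestinal form. Appendix 5 heads BEST as a questionnaire to "evaluar el impacto de los síntomas de un intestino irritable" on quality of life, scored from 0 (best) to 100 (worst).

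**Nearest specific objective.** Section 7.1 words it as "To evaluate the effect of cocoa supplementation on gastrointestinal symptoms".

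**Analysis.** Section 8.8 compares arms with an unadjusted t test or Mann-Whitney test at each measurement time. The sample size in 8.4 rests on the Toronto score (TCSS).

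**The concern.** The general claim is wider than both the selection and the measurement. Nothing at entry ensures that a participant has autonomic neuropathy, or identifies those who do. The two measures record bowel symptoms and stool form, which can arise from many causes.

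At stake is the conclusion that the trial is written to deliver. If BEST improves under cocoa, a report that follows the stated hypothesis would call this a benefit on autonomic neuropathy, although the data would show only a benefit on bowel symptoms. If BEST does not move, the same report would suggest no autonomic effect. Part of the sample may simply have had nothing to improve. The TCSS and H-reflex results are not affected.

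**Working it through.** **Step 1. Set the passages side by side.**

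| Element | Where | What it covers |
|---|---|---|
| Population and claim | Summary; 5, 6, 7 | Peripheral and autonomic neuropathy |
| Formal population | 8.3 | Diabetic neuropathy, type not stated |
| Entry criteria | 8.5 | Diabetic neuropathy, type not stated, plus MNSI of at least 2 |
| What MNSI detects | 2.5 | Peripheral neuropathy |
| Definition of autonomic neuropathy | 2.3, 8.6 | Cardiovascular, gastrointestinal, urogenital |
| Measures assigned to it | 8.6 | BEST and Bristol: gastrointestinal only |
| Bowel disease among the exclusions | 8.5 | None listed |
| Specific objective | 7.1 | Gastrointestinal symptoms |

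Two results follow. Entry does not require autonomic neuropathy. Of the three systems named in the plan's definition, one is assessed as an autonomic outcome, and by tools that do not separate neuropathy from other bowel conditions.

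**Step 2. Reproduce the plan's sample size.** Inputs from 8.4: SD 0.84, difference 0.776, Z values 1.96 and 0.84.

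2 × (1.96 + 0.84)² = 2 × 7.84 = 15.68

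15.68 × 0.7056 / 0.6021 = 18.4

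The plan states 18 per group (rounding up gives 19). With 18 per group a two-sample t test has about 77% power for this effect. The figure concerns the TCSS. The plan gives no effect, SD or power for BEST or Bristol.

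**Step 3. Illustrate the dilution (not an estimate).** Assumptions that are not in the documents:

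- The TCSS standardised effect, 0.776 / 0.84 = 0.92, carries over to BEST.
- It occurs only in participants with bowel symptoms at baseline.
- Their share f is 20%, 30% or 50%.

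The mean effect over all participants is then 0.92 × f. The result also depends on what is assumed about the spread.

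(a) SD held at 1 for everyone. The noncentrality is 0.924 × f × √(18/2) = 2.77 × f, with 34 degrees of freedom.

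(b) Change scores, where asymptomatic participants do not change at all and symptomatic ones have SD 1. The SD of change is √f in the control arm and √(f + f(1 − f) × 0.924²) in the cocoa arm. Power is by simulation, 18 per arm.

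| Share symptomatic | Expected per arm | Power (a) | Power (b) |
|---|---|---|---|
| 20% | 3.6 | 8% | 13% |
| 30% | 5.4 | 13% | 22% |
| 50% | 9 | 27% | 41% |
| 100% | 18 | 77% | 77% |

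The direction is the same under both models. The size is not fixed by anything in the documents.

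**The case against.** The strongest reply is that the plan is narrower than its headline. Section 2.5 admits that no standard exists and presents BEST and Bristol as gastrointestinal tools. Section 7.1 asks only about gastrointestinal symptoms. Sections 8.3 and 8.5 say diabetic neuropathy without further qualification. On this view the fault is one of labelling. That is largely right, and it is why the remedy is mainly wording. It does not remove the point, because the hypothesis and general objective are what a report answers to, and they still claim an autonomic effect.

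A reader might infer more than the documents support:

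- *That entry is limited to peripheral neuropathy.* It is not. Some participants may have autonomic neuropathy; none is required to.
- *That nothing cardiovascular or urogenital is recorded.* Blood pressure is taken monthly, and Diabetes 39 has a sexual-functioning section. The plan treats both as separate variables and assigns neither to autonomic neuropathy.
- *That a null would say nothing.* It would say something, to a degree that depends on the unknown share with symptoms. The floor argument applies to BEST. It does not carry over to Bristol, which runs from hard to watery stools and has no best end.
- *That power for the autonomic outcome is 8% to 27%.* Those figures borrow a peripheral-score effect, assume the shares and hold the SD fixed. Another defensible spread assumption gives about 13% to 41%.

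**Conclusion.** The point stands in this form. The autonomic claim in the summary, research question, hypothesis and general objective is not supported by the planned selection and measurement. The planned data can support a statement about gastrointestinal symptoms in patients with diabetic neuropathy selected by MNSI.

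This rests on the text of 2.3, 2.5, 7.1, 8.3, 8.5, 8.6 and Appendix 5, and on no outside figure. No size can be put on the loss of information from participants without bowel symptoms, because the plan gives neither their share nor a BEST effect or SD. The powers shown are an illustration under stated assumptions and should not be quoted as the trial's power. The documents do not support concluding that the trial as a whole is uninformative, or that it enrols no one with autonomic neuropathy.

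**What to change.** 1. **Claim.** In the summary and sections 5, 6 and 7, and in the title if it can still be changed, replace the effect on autonomic neuropathy with an effect on gastrointestinal symptoms, matching 7.1. Relabel the autonomic neuropathy row of the 8.6 table in the same way.
2. **Population.** In the summary, describe participants as patients with type 2 diabetes and diabetic neuropathy selected by MNSI, in line with 8.3 and 8.5.
3. **Analysis.** In 8.8, compare final BEST between arms adjusted for its baseline value, for example by analysis of covariance, with a rank-based version if the scores are skewed. This replaces the unadjusted comparison for that outcome.
4. **Reporting.** Give the baseline distributions of BEST and Bristol by arm, including the number scoring 0 on BEST, so that a null can be read properly.
5. **Optional.** An analysis restricted to participants symptomatic at baseline should be labelled descriptive and have its threshold stated in advance. At the shares illustrated it would hold about 4 to 9 per arm, and it can be left out.

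The cost is a narrower claim, an edit to several sections and one changed model. Section 8.7 already collects BEST and Bristol at baseline and at the end, so no visit, instrument or recruitment rule changes. The sponsor should confirm that the software named in 8.8 can fit the adjusted comparison.

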8.7 STRATEGIC PLAN

Through an open invitation, subjects living with T2D who meet the inclusion criteria will be invited to be assessed and tested at Anáhuac México Norte University, the Kidney Specialty Center, and the Nueva Oxtotitlán Clinic (Toluca), as appropriate. The invitation will be extended, explaining the procedures, duration, and ethical issues; if the subject decides to participate, he or she will be asked to sign the informed consent letter (Annex 1). Once the subject enters the protocol, he or she will be randomized (using a random number table previously generated in a spreadsheet) to the experimental group (diet + capsules with cocoa) or the control group (diet + capsules with methylcellulose).

The study will last three months and patients will be seen on four occasions: at the beginning (baseline measurement), at the first and second month (review appointments) and at the third month (final measurement).

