8.8 STATISTICAL ANALYSIS

A descriptive analysis of all dependent variables, as well as demographic variables, will be performed, expressing them as mean \pm standard deviation or, where appropriate, as median and range (min-max), according to the normality of the data; nominal variables will be expressed as frequencies. Subsequently, an intragroup inferential analysis will be carried out for weight, waist circumference, abdominal circumference and blood pressure with ANOVA for repeated samples with Tukey *post hoc*, and in case the data distribution does not meet the normality criteria, the corresponding nonparametric test will be performed (e.g.,

Friedman, followed by Dunn's *post hoc*). For biochemical analysis (glycemic and lipid profile and markers of inflammation), as well as the evaluations corresponding to diabetic peripheral and autonomic neuropathy, and quality of life, a Student's T test will be performed for dependent groups, or where appropriate, with Wilcoxon.

The intergroup comparison will be made with Student's T test for independent samples, or if applicable, with Mann-Whitney U at each measurement time. A $p < 0.05$ will be considered as statistical significance. All of the above will be carried out using version 5 of the GraphPad Prism software.

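### Participants are randomised at entry and then eliminated for later events, and no as-randomised month-3 analysis is planned; the two attendance rules overlap and need reconciling

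*Combined protocol and SAP*

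**What the plan says.** Section 8.7 (Strategic plan) fixes the order of events: "Once the subject enters the protocol, he or she will be randomized". Visits follow at months 1 and 2 (review) and month 3 (final).

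Section 8.5 has a list of elimination criteria, separate from the inclusion and non-inclusion criteria. Besides withdrawal of consent, it contains:

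- "Subjects who modify their pharmacological treatment during the study"
- "Subjects who do not attend one of the intermediate consultations"
- "Subjects with less than 80% adherence to cocoa supplementation"
- "Subjects who miss more than one consultation or do not attend the final consultation"

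Section 8.7 takes weight, circumferences and blood pressure monthly. It takes the TCSS, BEST, Bristol and Diabetes 39 instruments and the laboratory tests only at the beginning and the end.

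Section 8.8 compares the groups with Student's t test for "independent samples, or if applicable, with Mann-Whitney U at each measurement time". Neither section 8.8 nor the Summary names an analysis population, a rule for missing data, or a use for the data of eliminated participants. Section 8.4 derives 18 per group with no allowance for losses.

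**The concern.** Each elimination event happens after allocation. A comparison limited to people who kept their drugs stable, took at least 80% of their capsules and attended every visit is a comparison of self-selected subsets. Randomisation makes the full arms comparable, but it does not do so for these subsets. Drug changes may respond to glycaemia or blood pressure, which section 7.1 lists as outcomes, so that rule could select differently by arm if cocoa works.

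For the TCSS, laboratory tests and questionnaires, month 3 is the only post-baseline comparison, and it is where eliminated people would be absent. Someone who misses month 1 but attends month 3 has a complete baseline and final pair for these outcomes, yet one attendance rule removes that person. The two attendance rules also leave unclear what a single missed intermediate visit entails, and that should not be settled once data are in hand.

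**Working it through.** **1. Sequence and rules.** Randomisation is at entry (8.7). Drug change, adherence and attendance can be known only later (8.5), and section 8.8 has no analysis set that brings these people back. Values taken before elimination could still enter the tests at earlier times, but month-3 values would be missing if elimination ends follow-up, or unused if it means exclusion.

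**2. Attendance rules side by side.** There are three follow-up visits: months 1, 2 and 3. Missing more than one of them always includes missing month 1 or month 2. If missing one intermediate visit already eliminates, the limit of more than one catches nobody new among scheduled visits. Only the final-visit clause still adds anything.

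**3. Avoidable attendance loss.** The plan gives no rates. Assume each follow-up visit is missed independently with probability p.

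| Quantity | Formula | p = 0.05 | p = 0.10 |
|---|---|---|---|
| Final visit missed | p | 5.0% | 10.0% |
| Final attended, at least one intermediate missed | (1−p)[1−(1−p)²] | 9.3% | 17.1% |
| Final attended, exactly one missed | 2p(1−p)² | 9.0% | 16.2% |
| The same, of 36 people | 36 × row above | 3.2 | 5.8 |

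**4. The plan's sample size.** The last step in section 8.4 is 15.68 × 0.7056 / 0.6021 = 18.4, where 15.68 = 2(1.96 + 0.84)². The stated 18 is reproduced (19 if rounded up).

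**5. Power by t test.** Inputs from section 8.4: difference 0.776, SD 0.84, two-sided 5%. The noncentrality is (0.776/0.84)√(n/2) on 2n−2 degrees of freedom. At n = 18 it is 0.924 × 3 = 2.77 on 34 df.

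| n per arm | 18 | 17 | 16 | 14 | 13 |
|---|---|---|---|---|---|
| Power | 76.8% | 74.3% | 71.5% | 65.3% | 61.8% |

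With 5–10% missing month 3, 18 per arm becomes 17.1 to 16.2, so power is about 72–74%. The 16, 14 and 13 columns also show the effect of dropping 11%, 22% and 28% from both arms.

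**6. Dilution if non-adherers are kept.** Assume a share q of the cocoa arm is non-adherent and loses an amount g of the benefit. The difference becomes 0.776 − qg, and the cocoa-arm variance becomes 0.84² + q(1−q)g².

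| Power at q = 10/20/30% | 18 per arm | 17 per arm | 16 per arm |
|---|---|---|---|
| No benefit (g = 0.776) | 66/55/44% | 64/53/42% | 61/50/40% |
| Half benefit (g = 0.388) | 72/67/62% | 70/65/59% | 67/62/57% |

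At 18 per arm, against dropping a similar share from both arms (71.5/65.3/61.8%), keeping non-adherers costs about 5/10/18 points in the no-benefit case and roughly nothing in the half-benefit case.

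**The case against.** **Elimination is never defined as removal from the analysis.** This is true, and the point depends on the natural reading. Nothing in the documents supports the milder one: no section says eliminated people are followed up or analysed.

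**The attendance rules do not contradict each other.** A reader might infer a strict contradiction. The list gives sufficient grounds for elimination, and neither rule says that someone who misses one intermediate visit is kept. Both can be applied together, so the defect is redundancy and unclear wording.

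**The drug-change mechanism is speculative.** This stands in part. Trial glycaemia and HbA1c are taken only at the beginning and end, so they cannot prompt a mid-study change. Blood pressure is measured monthly, outside care can also prompt changes, and blinding lowers the chance of a difference between arms without excluding it. Section 8.6 lists hypoglycaemic drugs as a confounder, which may explain the rule, but section 8.8 does not use that variable. Keeping drug-changers does mix medication effects into the metabolic outcomes, so changes need reporting by arm.

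**The adherence rule names only cocoa.** A reader might infer that exclusion applies to one arm only. The trial is double-blind and both arms take capsules on the same schedule, so this is probably loose wording. No one-arm bias is claimed.

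**The trial is labelled explanatory.** Interest in the effect under adherence is legitimate, and a secondary per-protocol set serves it. That set does not replace the randomised comparison.

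**The remedy is also a subset.** This is correct: people without month-3 data remain absent, so the analysis must be called available-case.

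**18 is a calculated number, and no section states an enrolment target.** This also stands. The losses above assume that 18 per arm are enrolled.

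**Conclusion.** The concern holds in this form: rules that the plan states, if followed on their natural reading, turn the month-3 between-group tests into comparisons of post-randomisation subsets, and no as-randomised analysis is planned. This must be fixed, because no choice of test at month 3 restores comparability lost in this way.

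The documents do not support any figure for bias or inflated type I error. Such a figure would need an assumed difference in elimination between arms and an assumed link to outcome. The measurable part is the avoidable loss of complete pairs: about 3 to 6 of 36 for exactly one missed intermediate visit, assuming independent misses at 5–10% per visit. The power figures use the plan's own difference and SD; all missing-data and non-adherence rates are assumed.

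A reader might also infer that the repeated-measures ANOVA has to be replaced. In section 8.8 it is a within-group analysis of "weight, waist circumference, abdominal circumference and blood pressure with ANOVA for repeated samples with Tukey" post hoc comparisons, and changing it would not repair the between-group comparison. The H-reflex has no stated visit schedule, so the statement about discarded pairs does not extend to it.

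**What to change.** - Define the primary month-3 between-group analysis as all randomised participants with month-3 data, in their allocated arm, regardless of adherence, missed intermediate visits or drug change. Describe it as an available-case as-randomised analysis.
- Seek month-3 outcomes from everyone unless consent is withdrawn. If follow-up is finished, use all data already collected.
- Use the elimination rules only to define a secondary per-protocol set. Reconcile the two attendance rules, and word adherence as assigned capsules in both arms.
- Report eliminations, drug changes and missing month-3 values by arm and reason.
- Restate power for this analysis: 76.8% at 18 per arm with complete month-3 data, about 72–74% at 16–17 per arm, and lower with dilution.

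A mixed model for the monthly within-group measures is optional.

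The cost is protocol and SAP wording, plus month-3 visits or data recovery for people who would otherwise be dropped. The real downside is dilution by non-adherers, as tabulated above. People kept after only a missed intermediate visit need not dilute the effect. The change does not itself require more enrolment.
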